#### 7.5.4 Electrocardiograms

12 Lead ECG results and change from baseline will be summarized using mean, standard deviation, minimum, maximum and median for Enzalutamide, Placebo and Placebo crossover group at each visit. Baseline is defined as the last available measurement prior to the first dose (double-blind or open-label extension).

Number and percent of patients with normal, not clinically significant abnormal and clinically significant abnormal results for the 12 lead ECG will be tabulated by treatment arm and visit.

QTc will be calculated using Fridericia Formula, QTcF=QT interval /  $RR^{1/3}$ . Note: unit for RR is seconds.

All ECG results will be provided in a listing.

Any abnormal findings/conditions identified during the physical examination are reported in the medical history form or AE form. As a consequence, no separate physical examination listing can be produced.

#### 7.5.5 Pregnancy

Not applicable.

#### 7.5.6 Other Safety-Related Observations

The number and percentage of patients falling in each category of the performance status ECOG score will be summarized per visit and will be listed.

## 7.6 Analysis of Exploratory Endpoint

Not applicable.

## 7.7 Analysis of Pharmaco-kinetic

Not applicable

#### 7.8 Analysis of Pharmaco-dynamic

Not applicable.

#### 7.9 Subgroups of Interest

Subgroup analyses of OS will be conducted to assess the consistency of the treatment effect across the following subgroups of interest:

• Age category (less than 65 years old versus 65 years old or more);

- Geographic region (Europe, North America, Rest of the World);
- ECOG Performance Status (0 versus 1) at baseline;
- Gleason score (less than 8 versus 8 or more) at initial diagnosis;
- Disease location (bone only, versus soft tissue only, versus both bone and soft tissue) at baseline;
- Baseline PSA value (at or below overall median versus above overall median);
- Volume of disease at baseline (low versus high)
- Prior docetaxel use (yes versus no)
- Previous use of ADT or orchiectomy (yes versus no)

#### 7.10 Other Analyses

Not applicable.

#### 7.11 Interim Analysis (and Early Discontinuation of the Clinical Study)

Not applicable

# 7.12 Handling of Missing Data, Outliers, Visit Windows, and Other Information

The baseline measurement is the last measurement taken prior to initial study drug administration (double-blind or open-label extension). Both date and time of drug administration and measurement should be considered to identify the baseline value. If the time is not available, then date only will be used, and it will be considered that assessments on day 1 are done pre-dose.

Change from baseline is defined as (post baseline value - baseline value).

To calculate time interval duration, a month is 30.4375 days and a year 365.25 days. Duration expressed in years or months are rounded up to 1 significant digit. The duration between 2 dates d1 and d2 is (d2-d1+1) in days (with d1 before d2).

Treatment day and study day will be calculated in reference to the date of the first dose of study drug. Treatment Day 1 corresponds to the date the patient received the first dose of study drug. For assessments conducted on or after the date of the first dose of study drug, treatment day will be calculated as (assessment date - date of first dose of study drug) + 1. There will be no Treatment Day 0.

Unless otherwise specified, the date of study drug discontinuation refers to the study drug last dose date.

Time to event endpoints will be based on the actual date of event rather than visit date. The date of randomization will always be considered as the start date for the time interval.

For laboratory results collected as < or > a numeric value, 0.000000001 will be subtracted or added, respectively, to the value unless otherwise specified.

Percentages will be calculated based on the number of patients with non-missing data as the denominator unless otherwise specified.

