#### 6.3 Treatment Emergent Adverse Event (TEAE)

A TEAE is defined as an AE that occurs or worsen at any time during the treatment emergent period. The treatment emergent period is time interval encompassing the double-blind treatment emergent period and the OLE treatment emergent period.

The double-blind treatment emergent period is defined as the time interval from the first double-blind study drug intake up to 30 days after the date of the last dose of double-blind study drug, study discontinuation, the start of new antineoplastic therapy, or the first dose of OLE treatment, whichever occurs first.

If AE start date is the same date as the study start, then it will be considered as a TEAE if the box 'Onset after first dose of study' is ticked in the Electronic case report form(eCRF). If a patient experiences an event both during the pre-investigational period and during the investigational period, the event will be considered as TEAE only if it has worsened in severity (i.e. it is reported with a new start date).

The OLE treatment emergent period is defined as the time interval from the OLE study drug intake up to 30 days after the date of the last dose of OLE study drug, study discontinuation, or the start of new antineoplastic therapy, whichever occurs first.

AE with both a missing start and stop dates, and AEs with a missing start date but has a known stop date which is on or after the first dose of study drug will be considered treatment-emergent.

For each treatment group, the treatment emergent period is as follows;

- Enzalutamide group: from the first DBT study drug intake up to 30 days after the date of the last dose of study drug, study discontinuation, or the start of new antineoplastic therapy, whichever occurs first.
- Placebo group: from the first DBT study drug intake up to 30 days after the date of the last dose of placebo, start of open-label enzalutamide, study discontinuation, or the start of new antineoplastic therapy, whichever occurs first.
- Placebo crossover group: from the first OLE study drug intake up to 30 days after the date of the last dose of OLE study drug, study discontinuation, or the start of new antineoplastic therapy, whichever occurs first.

AEs will be coded to System Organ Class (SOC) and preferred term using MedDRA v23.0 and severity graded using National Cancer Institute's Common Terminology Criteria version 4.03 (NCI-CTCAE v4.03) for AEs.

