#### 7.3 Study Drugs

#### 7.3.1 Exposure

The following information on drug exposure will be presented for Enzalutamide, Placebo and Placebo crossover group on the SAF.

- The duration of exposure (number of months) to study medication will be summarized using descriptive statistics, including 10%, 25%, 75% and 90% percentiles.
- Number and percentage of patients on study drug at 6 months and at year 1, 2, 3, and 4 (that is with duration of exposure superior or equal to day 182, 365, 730, 1095, and 1461).
- Number and percent of patient with dose reductions or interruptions, the reasons for these, as well as the number of these per patient
- Descriptive statistics for the average daily dose of the drug patient was exposed to
- Time to study drug discontinuation will be analyzed using the same analysis methods as OS, but formal statistical test will not be conducted.

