The number and percentage of patients with TEAEs, as classified by SOC and preferred terms will also be summarized by maximum severity (reported according to NCI-CTCAE version 4.03).

In the patient count, if a patient has multiple TEAEs with the same SOC or PT, but with different severity, then the patient will be counted only once with the worst severity. However, if any of the severity values are missing then the patient will be counted only once with missing severity. In the AE count, the AEs will be presented in each category they were classified to. Summaries will be provided for:

- TEAEs by NCI- CTCAE
- drug related TEAEs by NCI- CTCAE,
- serious TEAEs by NCI- CTCAE

The number and percentage of patients with TEAEs that equal to or exceed a threshold of 5.0% in any treatment group, classified by preferred terms (by decreasing frequency within the enzalutamide group) will be summarized by treatment group and time interval. The percentage of patients are calculated based on the number of patients still on treatment at the time-point corresponding to the lower limit of the time intervals. Time intervals will be categorized according to the following categories:

- $\leq$ 3 months;
- >3 months to  $\leq 6$  months;
- >6 months to  $\leq 12$  months;
- >12 months to  $\leq$ 24 months;
- >24 months to  $\leq$ 36 months;
- >36 months.

To adjust for the treatment duration, the number of TEAEs per 100 patients-years will be summarized, as classified by SOC and PT, per treatment group and CTI-CTC grade (3-5 and total). The number of TEAEs per 100 patients-years is calculated as the number of events

\*100 / (sum of the treatment emergent period duration of all patients treated in the corresponding treatment group, in years).

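### The SAP's rounding rule for durations is wrong as written: it makes the month-based exposure summaries unusable and leaves the patient-year denominators open to an unequal bias

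*SAP*

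**What the plan says.** SAP 7.12 gives the general conventions for durations in one short paragraph. It first sets the conversion constants: "To calculate time interval duration, a month is 30.4375 days and a year 365.25 days". The next sentence is the rounding rule, "Duration expressed in years or months are rounded up to 1 significant digit". The paragraph ends with the base formula, an inclusive count of days, d2 − d1 + 1. Nothing confines the rounding to display.

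Two planned outputs use durations in these units:

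- SAP 7.3.1: "The duration of exposure (number of months) to study medication will be summarized using descriptive statistics", with the 10th, 25th, 75th and 90th percentiles.
- SAP 7.5.1: the exposure-adjusted adverse event rate, events × 100 divided by the "sum of the treatment emergent period duration of all patients treated in the corresponding treatment group, in years". No rounding step is mentioned, either before or after the sum.

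The treatment-emergent period differs by group (SAP 6.3). For enzalutamide it runs across the double-blind and open-label periods. For placebo it runs "up to 30 days after the date of the last dose of placebo, start of open-label enzalutamide, study discontinuation". Beginning another cancer treatment also closes the placebo period, and the earliest of these dates counts.

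**The concern.** The rule stands among the derivation rules, between the constants and the formula, so a programmer may reasonably apply it to the derived variable. One significant digit is far too coarse for exposures of one to four years. In months it leaves only 10, 20, 30 and so on; in years it leaves whole numbers above one year.

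Rounding upwards is also one-sided, so the error does not average out over patients. If it is applied patient by patient, it adds proportionally more to a group whose exposures are mostly one to two years than to a group with longer exposures. The placebo period is closed at open-label start at the latest, so placebo is probably the shorter group. Its rates would then be lowered more than those of enzalutamide, in the table meant to adjust for unequal treatment duration.

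**Working it through.** **No figure to reproduce.** Neither document gives exposure times or a patient-year total for the groups in this SAP, so there is no stated figure to recompute. The rule can be applied to single durations exactly. Its effect on group totals needs assumed exposures.

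**Step 1. Single durations.** Months = days / 30.4375 and years = days / 365.25 (SAP 7.12), then rounded up to one significant digit.

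| Days | Months | Rounded up | Years | Rounded up |
|---|---|---|---|---|
| 365 | 11.99 | 20 | 0.999 | 1 |
| 366 | 12.02 | 20 | 1.002 | 2 |
| 400 | 13.14 | 20 | 1.095 | 2 |
| 730 | 23.98 | 30 | 1.999 | 2 |
| 1095 | 35.98 | 40 | 2.998 | 3 |

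One extra day takes a patient from 1 year to 2. A patient with 730 days has 2 years in one unit and 30 months (30 / 12 = 2.5 years) in the other. Ordinary rounding to one significant digit does not rescue the month summaries: 400 days becomes 10 months, and 55 months still becomes 60.

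**Step 2. Patient-years, if each patient is rounded before summing.** Let b be the relative inflation of a group's patient-years. Its rate, 100 × events / patient-years, is multiplied by 1 / (1 + b). The enzalutamide:placebo rate ratio is multiplied by (1 + b placebo) / (1 + b enzalutamide).

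Assumed, not in the documents: 200,000 simulated patients per group, exponential discontinuation with mean 5 / 2 / 4 years (enzalutamide / placebo / placebo crossover), and a uniform administrative cap of 3.5–4.9 / 1–2.3 / 1.8–2.6 years. The resulting mean durations are 2.83 / 1.11 / 1.69 years.

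| Reading of the rule | Enzalutamide | Placebo | Crossover | Rate ratio multiplied by |
|---|---|---|---|---|
| Up, 1 significant digit | +14.4% | +34.9% | +26.1% | 1.349 / 1.144 = 1.18 |
| Nearest, 1 significant digit | +1.2% | −2.7% | −3.0% | 0.96 |
| Up, 1 decimal | +1.8% | +4.6% | +3.0% | 1.03 |
| Nearest, 1 decimal | 0.0% | 0.0% | 0.0% | 1.00 |

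Under the first reading the rates are multiplied by 0.87, 0.74 and 0.79.

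Hand check of the third row: rounding up to 0.1 year adds about 0.05 year per patient. That gives 0.05 / 2.83 = 1.8%, 0.05 / 1.11 = 4.5% and 0.05 / 1.69 = 3.0%.

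**Step 3. Sensitivity to the assumed exposures (up, 1 significant digit).** With means of 2.4 / 1.2 / 1.4 years the inflation is 17% / 30% / 29%, and the rate ratio is multiplied by 1.30 / 1.17 = 1.11. Over other assumed means:

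| Mean (years) | 0.69 | 1.05 | 1.23 | 1.88 | 2.90 | 3.52 |
|---|---|---|---|---|---|---|
| Inflation | 27.5% | 34.9% | 29.3% | 21.3% | 15.4% | 14.3% |

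This gives about 14 to 17% for means of 2.4 to 3.5 years and about 27 to 35% for means of 0.7 to 1.2 years. The inflation does not keep rising as exposure shortens, because durations under one year are rounded in tenths. Over the same means, rounding up to one decimal gives 1.4% to 7.4%.

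**Step 4. Rounding after summing.** If patient-years are summed unrounded and only the total or the displayed value is rounded up to one decimal, the effect is negligible.

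**The case against.** The best defence is that nobody would program the rule literally. The SAP itself uses 55 months and a 15-month difference in its sample size section, and neither can be written with one significant digit. Percentiles of exposure make no sense in multiples of ten. Durations are first derived in days, and the exposure landmarks are set in days ("that is with duration of exposure superior or equal to day 182, 365, 730, 1095, and 1461"), so the rule does not touch them. Summing days and converting once fits the definition in 7.5.1. A duration expressed in a unit can also be read as a matter of presentation. The table specifications and the main-study SAP may settle the point, but they are not among the documents.

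Most of this stands. One decimal place was probably intended, and the order of rounding and summing is open. But the harmless reading departs from the text twice: up must not mean up, and a significant digit must mean a decimal place.

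A reader might go further and infer that every exposure-adjusted rate is distorted. The documents do not support that. It requires the literal ceiling, the literal significant digit, and rounding per patient before the sum, and the last is nowhere stated. A reader might also take the patient-year rate to be the only adjustment for longer enzalutamide observation. It is not: SAP 7.5.1 also tabulates the more frequent events (5% or more in any group) by time interval, using as denominator the patients still on treatment at the start of each interval.

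**Conclusion.** Wrong as written, minor severity.

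- **Exposure in months (7.3.1).** If the significant digit is taken at its word, the summaries are unusable, whether values are rounded up or to the nearest. This needs no assumption about exposure times.
- **Patient-years (7.5.1).** The effect is conditional on rounding each patient before summing. It then ranges from about 0% (nearest decimal) through about 2 to 5% (up to one decimal) to roughly 14 to 17% for enzalutamide and 27 to 35% for placebo (up to one significant digit). The sizes, and the direction of the difference between groups, rest on assumed exposures.

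These outputs are descriptive. A reader might extend the point to overall survival, but the SAP does not give the unit of the survival time variable, so the documents do not show an effect there.

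**What to change.** Replace the rounding sentence in SAP 7.12 with:

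> Durations are computed in days and converted without rounding (days/30.4375 or days/365.25) for all analyses, sums and rates; rounding to one decimal place is applied only for display.

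This removes the rounding bias from patient-years by construction and gives every programmer the same denominator. It costs one sentence and changes no endpoint, test or data collection. If the programs already work from unrounded days, the change only brings the text into line with them.

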#### 6.1 Overall Survival

OS is defined as the time from randomization to death from any cause. All deaths on or before the data cut-off will be included.

For patients who are alive at the time of the cut-off date, OS time will be censored on the last date the patient is known to be alive or the cut-off date, whichever occurs first. The date the patient is last known alive by the cut-off date will be derived as follows:

- for patients on treatment by the cut-off date (i.e., patients who did not discontinue from treatment), the date last known alive will be the cut-off date.
- for patients who withdraw consent by the cut-off date, the date last known alive is the date of consent withdrawal.
- for patients lost to follow up, the date last known alive depends on the period the patient was lost to follow-up. It will be as follows:

Period lost to follow-up	The date last known alive		
Since randomization (i.e. without	The date of randomization		
further post-randomization visit)			
During treatment period	The last assessment/visit date or the date of the last		
	dose of study drug, whichever occurs later		
Safety follow-up period	The date of the last dose of study drug or the last		
	treatment visit date collected on the End of Treatment		
	Case Report Form (CRF) page, whichever occurs last.		
Long-term follow-up period	The last visit/contact date (collected either on the		
	30 Day Follow-Up Status CRF page, or the Patient		
	Status - Survival CRF page or the Long-Term Follow-		
	Up Status CRF page).		

• for other patients (i.e., not on treatment, not withdrawn and not lost to follow-up) who are alive by the cut-off date, the date last known alive is the date of last visit (collected either on the Patient Status - Survival CRF page or the Long-Term Follow-Up Status CRF page) or the date of randomization, whichever occurs last.

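### As written, the SAP starts time to study drug discontinuation at randomization for the Placebo crossover group, so placebo time counts as persistence on enzalutamide

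*SAP*

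**What the plan says.** Three SAP rules meet here.

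- **Who is analysed.** SAP 7.3.1 opens: "The following information on drug exposure will be presented for Enzalutamide, Placebo and Placebo crossover group on the SAF". One item on its list reads: "Time to study drug discontinuation will be analyzed using the same analysis methods as OS, but formal statistical test will not be conducted".
- **Start of the clock.** SAP 7.12, on time-to-event endpoints, says: "The date of randomization will always be considered as the start date for the time interval". The OS methods that 7.3.1 borrows belong to a variable with the same origin (SAP 6.1): "OS is defined as the time from randomization to death from any cause".
- **End of the clock.** SAP 7.12 adds: "Unless otherwise specified, the date of study drug discontinuation refers to the study drug last dose date".

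Elsewhere the SAP does give the open-label period its own start. SAP 6.3 begins the crossover group's treatment-emergent period at the first open-label dose. It closes the Placebo group's period no later than the start of open-label enzalutamide. The baseline rule in 7.12 recognises an open-label first dose, and the notes to Table 4 in 7.12.3 define an OLE baseline and OLE week labels. Time to study drug discontinuation has no matching rule.

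**The concern.** A placebo subject joins the Placebo crossover group only by starting open-label enzalutamide. Protocol 12.6.3 requires that he received randomized treatment and met no discontinuation criterion. Protocol 12.6.4 excludes placebo subjects who progressed radiographically and whose study drug was stopped before study-wide unblinding. If the clock starts at randomization, the interval up to the first open-label dose is immortal time: membership of the group guarantees that no discontinuation of enzalutamide happens in it, and the drug taken was placebo. The resulting curve does not describe how long these men stayed on enzalutamide.

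The curve for the Placebo group has a related gap. The same men were randomized to placebo, and the SAP does not say how their switch is handled there.

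At stake is how readers judge tolerability and persistence after crossover. SAP 1 names the incorporation of these subjects as one purpose of the document.

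**Working it through.** There is no stated figure to reproduce, since the point concerns a definition. I set the rules side by side and then illustrated the size.

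**1. Effect of the origin.** Let *T* be the time from first open-label dose to last dose, and *L* the time from randomization to first open-label dose. The 7.12 rule analyses *T + L* where the group calls for *T*. Then S_rand(t) = E[S_OLE(t − L)], with S_OLE equal to 1 for negative arguments. Because *L* > 0, S_rand(t) is never below S_OLE(t), and it equals 1 up to the shortest lead-in. The direction therefore needs no assumption about *L*.

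**2. One subject.** Inputs: a month is 30.4375 days (SAP 7.12); *L* is not in the documents and is varied from 6 to 36 months. A subject stops on open-label day 183.

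- From the first open-label dose: 183 / 30.4375 = 6.0 months.
- From randomization, 6.0 + *L*: 12.0, 18.0, 24.0, 30.0 and 42.0 months for *L* = 6, 12, 18, 24 and 36.

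**3. The curve.** Assume exponential *T* and uniform *L*, and solve E[S_OLE(t − L)] = 0.5.

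| Assumed true median (months) | Assumed lead-in (months) | Median from randomization (months) |
|---|---|---|
| 18 | 9 to 21 | 33.2 |
| 18 | 18 to 36 | 45.5 |
| 24 | 6 to 18 | 36.2 |
| 24 | 12 to 36 | 48.7 |
| 30 | 9 to 21 | 45.1 |
| 30 | 18 to 36 | 57.3 |

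The inflation is roughly the mean lead-in. With a true median of 18 months, the true 12-month on-drug rate is 2^(−12/18) = 63%. The randomization clock would show 99% (lead-in 9 to 21) or 100% (18 to 36).

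**4. Placebo group.** The event is the last dose of study drug, and SAP 7.2.4 uses that term for enzalutamide or placebo. Three codings are open for a switcher: run on to the last open-label dose, count the switch as an event, or censor at the switch. As an example, assume a true median of 15 months on placebo, exponential, with λ = ln 2 / 15, and switch times uniform over 9 to 30 months. The proportion switching is (e^(−9λ) − e^(−30λ)) / (21λ) = 42%. If the switch is an event, the median solves e^(−λt)(30 − t)/21 = 0.5, giving 11.8 months. Censoring recovers 15. The SAP does not say which coding applies.

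**5. AE time-interval table (SAP 7.5.1).** Frequent TEAEs "will be summarized by treatment group and time interval", in bins from up to 3 months to beyond 36 months. No time zero is given. An AE on open-label day 30 falls in the first bin on the open-label clock. On a first-placebo-dose clock it would fall in >6–12 months (*L* = 6), >12–24 (*L* = 12 or 18), >24–36 (*L* = 24) or >36 (*L* = 36). The sentence on the randomization origin does not govern this table, and nothing states that the bins use the placebo clock.

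**The case against.** The strongest reply is that time to study drug discontinuation is not an endpoint in the SAP's own sense. The key terms define an endpoint as a variable tied to the trial objectives, and SAP 3.1 names OS, supportive time to new antineoplastic therapy, and safety. Discontinuation time sits under exposure. Borrowing the OS methods could mean the Kaplan-Meier and Cox machinery of 7.4.1 and not the origin in 6.1. Protocol 12.6.7 asks for enzalutamide exposure to be summarized in the open-label extension, which suggests that the authors did not mean to count placebo time. SAP 7.2.1 reports discontinuations separately by period, and 7.3.1 also gives duration of exposure, so persistence does not rest on this curve alone. SAP 6 refers to a primary-analysis SAP for variable definitions, and that document is not available here.

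Much of this bears on intent, and it limits the harm. It does not remove the word *always* or supply another origin. The main SAP was completed before unblinding, and SAP 1 presents this supplement as the place where crossover summaries are added, so the rule belongs here.

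Two stronger readings are tempting and should be resisted.

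- **That crossover AE timing is wrong as written.** A reader might infer this because "Treatment Day 1 corresponds to the date the patient received the first dose of study drug", and for these men the first dose was placebo. But 7.5.1 does not tie its bins to treatment day, and 6.3 starts the crossover treatment-emergent period at the first open-label dose. TEAE attribution and rates per 100 patient-years are therefore correctly anchored. The bins have an unstated clock, not a demonstrated error.
- **That the Enzalutamide curve is also distorted.** Those subjects are randomized on day 1, just before treatment begins (Protocol 4.5 and Table 1), so the two origins nearly coincide. No mechanism for distortion is apparent.

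**Conclusion.** The point stands for one output. Under SAP 7.12 and 7.3.1 as worded, time to study drug discontinuation in the Placebo crossover group runs from randomization and overstates persistence on enzalutamide by the pre-crossover period. The direction follows from the definition. The size does not, because the documents give no lead-in times, and the medians above are illustrations under assumed values.

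The Placebo group lacks a rule for switchers, which is an omission with several possible readings. The AE interval table needs its time zero stated and no more than that.

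All of these outputs are descriptive. SAP 7.3.1 rules out a formal test of discontinuation time, and the OS analysis, properly timed from randomization, is untouched. The correction is worth making before the tables are produced, but it does not threaten the trial's main conclusion.

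**What to change.** In SAP 7.3.1 and 7.12:

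1. State that, for the Placebo crossover group, time to study drug discontinuation starts at the first dose of open-label enzalutamide.
2. Limit the randomization-origin sentence in 7.12 to OS and the other comparisons by randomized arm, such as time to new antineoplastic therapy.
3. State that, in the Placebo group, subjects who switch are censored at the last placebo dose, or at the first open-label dose if that is earlier. This matches the treatment-emergent period in 6.3.

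In SAP 7.5.1, as a clarification, state that the AE time-interval bins and their denominators for the crossover group run from the first open-label dose.

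The cost is a few sentences and one derived start date. The first open-label dose date is already needed for the treatment-emergent period in 6.3, so no new data are collected.
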